During this 4-week Treatment Period, study drug will be self-administered, orally, once a day, in the morning, without regard to food. Subjects will continue to document the presence and maximum severity of daytime and nighttime heartburn symptoms and record usage of rescue medication using an eDiary. Subject visits will be conducted at Weeks 2 and 4 of the Treatment Period to collect and/or dispense study drug, assess GERD symptoms, review concomitant medication use, assess adverse events and subject will undergo a physical examination including vital signs. In addition, at the Week 4/ Final Visit, all subjects will undergo laboratory evaluations, ECG, fasting serum gastrin and urine pregnancy test (all women of childbearing potential). Subjects who prematurely discontinue during the study after the randomization should undergo Week 4/Final Visit procedures no later than 5 days after the last dose of study drug.

A schematic of the study design is included as Figure 6.a. A schedule of assessments is listed in Appendix A.

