5.2.5 Definition of Study Days and Visit Window

Study day was calculated relative to the date of the first dose of study drug in the study. The study day prior to the first dose of study drug was calculated as:

$$\text{Date of assessment/event} - \text{date of first dose of study drug}$$

The study day on or after the first dose of study drug was calculated as:

$$\text{Date of assessment/event} - \text{date of first dose of study drug} + 1.$$

The visit windows for the post baseline visits were defined in [Table 5.a](#). If a subject had more than 1 measurement in the same visit window, the measurement closest to the scheduled visit was used. If 2 measurements in the same window were of equal distance to the scheduled visit, the measurement that occurred after the scheduled visit was used. If 2 or more measurements occurred on the same day, the last value obtained was used.

Table 5.a Visit Window

Visit	Scheduled Day	Safety Labs & Serum Gastrin	Vital Signs	ECG	GERD Symptoms Investigator Assessment
Baseline	Day -1	≤1	≤1	≤1	≤1
Week 2	Day 14	2-21	2-21	NA	2-21
Week 4	Day 28	22-35	22-35	2-35	22-35

Note: Safety labs (including gastrin), vital signs, and ECG data obtained more than 7 days after the last day of study drug and efficacy data obtained more than 7 days after the last day of study drug weren’t included in the analyses.

Diary entries were assigned to study days according to the beginning of the recall period. Specifically, entries completed in the evening (reporting heartburn during the day) were assigned

to the same day; entries completed in the morning (reporting heartburn during the night) were assigned to the previous day.

For the purpose of diary compliance calculation and derivation of diary-based endpoints, the last day of study drug wasn't included since the subject was not expected to have completed the diary entries for that day by the Week 4/Final Visit. Therefore, summaries for the 4 weeks of treatment included Study Day 1 through Study Day 35 or the day before the last dose of study drug, whichever occurred first.

For efficacy variables summarized by visit, the value closest to the last day of study drug was summarized for each subject, including those within 7 days of the last day of study drug. If 2 measurements were of equal distance to the last day of study drug, the later measurement was used.

AEs that started more than 30 days after the last dose of study drug were listed, but excluded from the summaries and analyses.

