6.0 STUDY RESULTS

6.1 Disposition of Subjects

A total of 325 subjects were screened. Of the subjects screened, 108 (33.2%) were ineligible for entrance into the treatment period. The primary reasons for screen failure were subject did not meet entrance criteria (80.6%), withdrawal by subject (13.9%), and other reasons (5.6%).

Of the subjects screened, 217 (66.8%) entered the treatment period at 20 sites in China: 108 subjects were randomized to the dexlansoprazole capsules group and 109 subjects were randomized to the placebo group. Of note, one subject in each group never received any study drug.

A total of 10 subjects prematurely discontinued study drug, and 205 subjects completed all the study drug and planned study visits.

Overall subject disposition is presented in [Table 6.a](#), and a flow chart is presented [Figure 6.a](#). By-subject listings of screen failures and subject disposition are provided in Appendix 16.2.1.2 and 16.2.1.3.

Table 6.a Overall Disposition of Subjects

	Placebo QD N (%)	Dexlansoprazole 30 mg QD N (%)	Total N (%)
Subject Screened			325
Subjects Eligible for Entrance Into Treatment Period (a)			217 (66.8)
Randomized But Not Treated (b)	1 (<1)	1 (<1)	2 (<1)
Completed Study Drug (b)	102 (93.6)	103 (95.4)	205 (94.5)
Prematurely Discontinued Study Drug (b)	6 (5.5)	4 (3.7)	10 (4.6)
Completed All Planned Study Visits (b)	102 (93.6)	103 (95.4)	205 (94.5)
Did Not Complete All Planned Study Visits (b)	7 (6.4)	5 (4.6)	12 (5.5)
Subjects Not Eligible for Entrance Into Treatment Period (a)			108 (33.2)
Primary Reason Subject not Eligible for Treatment Period (c)			
Adverse Event			0
Significant Protocol Deviation			0
Lost to Follow-up			0
Withdrawal by Subject			15 (13.9)
Study Termination by Sponsor			0
Pregnancy			0
Did not Meet Inclusion Criteria or Did Meet Exclusion Criteria			87 (80.6)
Other			6 (5.6)

[figure not shown]
Source: Table 15.1.3 and Table 15.1.5.

(a) Denominator of the percentage is the number of subjects screened.

(b) Denominator of the percentage is the total number of subjects who are eligible for entrance into treatment period.

(c) Denominator of the percentage is the total number of subjects who aren't eligible for entrance into treatment period.

Figure 6.a Flow Chart of Subject Disposition

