8.2 Clinical Laboratory Evaluation

8.2.1 Hematology

By-subject hematology parameters result are presented in Appendix 16.2.8.1.1 and the out-of-normal-range results are presented in Appendix 16.2.8.1.5.

Descriptive statistics for baseline, post baseline, and change from baseline to post baseline values for relevant hematology parameters are summarized in Table 15.3.4.1.3. Mean changes from baseline in hematology parameters in both groups were small and were not clinically concerning.

Some shifts from baseline to week 4 in hematology values were observed in both treatment groups and are summarized in Table 15.3.4.1.5. These shifts occurred in few subjects overall, and none were clinically concerning.

Hematology MAVs are summarized in Table 15.3.4.1.7.1 and listed in Appendix 16.2.8.1.8. No subjects in the dexlansoprazole group had hematology MAVs during treatment. Two subjects in the placebo group had hematology MAVs at week 4. One subject had markedly abnormally low hemoglobin (<88g/L). The second subject had markedly abnormally low platelets (<75×10³/μL). The hematology MAVs were not reported as AEs.

No subject had abnormalities in hematology parameters that were classified as SAEs.

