8.2.4 Serum Gastrin

The percentages of subjects with elevated gastrin values ≥200 pg/mL and ≥400 pg/mL are presented in Table 8.c. The number and the percentage of subjects with elevated gastrin values was greater in the dexlansoprazole capsules group than in the placebo group at week 4.

Descriptive statistics for baseline, post baseline, and change from baseline to post baseline values for gastrin are summarized in Table 15.3.4.1.10. The mean change value in the dexlansoprazole capsules group (73.9 pg/mL) were greater than those in the placebo group (-3.8 pg/mL) at week 4.

Table 8.c Summary of Gastrin Results (Safety Analysis Set)

	No. of Subjects (%)	
	Placebo QD N=108	Dexlansoprazole 30 mg QD N=107
Elevated Gastrin Values		
No. of Subjects at Visit 4 (Week 4)	102	103
≥200 pg/mL	6 (5.9)	15 (14.6)
≥400 pg/mL	3 (2.9)	4 (3.9)

Source: Table 15.3.4.1.8.

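### SAP Table 5.a gives safety labs and gastrin a Week 2 window although no labs are scheduled then, so Final Visit samples taken by Day 21 drop out of the Week 4 summaries (minor)

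*SAP*

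**What the plan says.** **Schedule.** Protocol 6.1 states that "at the Week 4/ Final Visit, all subjects will undergo laboratory evaluations, ECG, fasting serum gastrin and urine pregnancy test". The Week 2 procedure list (Protocol 9.3.3.2) contains no laboratory tests, gastrin or ECG, and Appendix A agrees. The only other post-dose gastrin is at unscheduled visits (Protocol 9.3.5). Subjects who stop early "should undergo Week 4/Final Visit procedures no later than 5 days after the last dose of study drug" (Protocol 6.1).

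**Windows.** The columns of SAP Table 5.a (Section 5.2.5) are, in order, "Safety Labs & Serum Gastrin", vital signs, ECG, and the investigator's GERD symptom assessment. The two post-dose rows read "Week 2 Day 14 2-21 2-21 NA 2-21" and "Week 4 Day 28 22-35 22-35 2-35 22-35". Within a window, the measurement closest to the scheduled day is used. Labs taken more than 7 days after the last day of drug are excluded. A separate rule in the same section takes the value closest to the last day of drug, but only for efficacy variables.

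**Results.** SAP 6.1 reports that "205 subjects completed all the study drug and planned study visits". Table 8.c (SAP 8.2.4) has a row beginning "No. of Subjects at Visit 4 (Week 4", with 102 placebo and 103 dexlansoprazole subjects. SAP 8.2.1 words its shift summary in the same way: "Some shifts from baseline to week 4 in hematology values were observed in both treatment groups". Section 8.2.2 does likewise for chemistry.

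**The concern.** Labs, gastrin and ECG share one planned post-dose visit. Table 5.a handles that correctly for ECG. For labs and gastrin it uses the split that suits vital signs and GERD symptoms, both of which really are collected at Week 2. No reason is given for the difference.

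The rule therefore assigns data to a visit that does not collect them. Early stoppers are asked back for Final Visit procedures, including labs. If that visit falls on or before Day 21, the sample carries a Week 2 label and does not contribute to any table labelled Week 4. Nothing in Section 5.2.5 brings it back, because the value-closest-to-last-dose rule does not extend to safety data. At stake is whether the Week 4 gastrin, shift and mean-change tables use every end-of-treatment sample available in the safety analysis set.

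**Working it through.** **1. Windows against schedule**

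| Assessment | Collected at Week 2? | Week 2 window | Week 4 window |
|---|---|---|---|
| Safety labs, gastrin | No | Days 2-21 | Days 22-35 |
| ECG | No | NA | Days 2-35 |
| Vital signs | Yes | Days 2-21 | Days 22-35 |
| GERD symptoms | Yes | Days 2-21 | Days 22-35 |

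Only the first row has a Week 2 window without a Week 2 collection.

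**2. What decides the label.** It is the day of the sample, not the day of stopping. The Final Visit may be up to 5 days after the last dose, so a subject who stops on Day 17 can be sampled on Day 17 + 5 = Day 22 and still count as Week 4. A subject sampled on Day 21 or earlier does not.

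**3. Reproducing Table 8.c** (percentage = n/N × 100)

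- At least 200 pg/mL: placebo 6/102 = 5.88%, printed 5.9; dexlansoprazole 15/103 = 14.56%, printed 14.6.
- At least 400 pg/mL: placebo 3/102 = 2.94%, printed 2.9; dexlansoprazole 4/103 = 3.88%, printed 3.9.

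All four agree.

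**4. Comparing denominators**

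| | Placebo | Dexlansoprazole | Total |
|---|---|---|---|
| Safety analysis set (SAP 6.3) | 108 | 107 | 215 |
| Stopped study drug early (Table 6.a) | 6 | 4 | 10 |
| Completed all visits (Table 6.a) | 102 | 103 | 205 |
| Week 4 gastrin N (Table 8.c) | 102 | 103 | 205 |

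**5. How many samples exist outside the Week 4 row.** The SAP's description of amendments shows a superseded during-treatment row. It is used here only as evidence of how many values there were; its removal is not an error. It gives 6 (5.7%) and 3 (2.8%) on placebo, and 15 (14.3%) and 4 (3.8%) on dexlansoprazole. The only whole-number denominators up to the arm size that reproduce both percentages are:

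- Placebo 106: 6/106 = 5.66% and 3/106 = 2.83%. At 105, 3/105 = 2.86% rounds to 2.9; at 107, 6/107 = 5.61% rounds to 5.6.
- Dexlansoprazole 105: 15/105 = 14.29% and 4/105 = 3.81%. At 104, 15/104 = 14.42% rounds to 14.4; at 106, 15/106 = 14.15% rounds to 14.2.

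Differences: 106 − 102 = 4 placebo and 105 − 103 = 2 dexlansoprazole, 6 in all against 10 early stoppers.

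**6. Effect on gastrin.** The elevated counts are the same in both rows (6 and 15; 3 and 4), so none of the six extra subjects reached 200 pg/mL. Counting them moves placebo from 5.9% to 5.7% and dexlansoprazole from 14.6% to 14.3% at the 200 threshold, and from 2.9% to 2.8% and 3.9% to 3.8% at the 400 threshold.

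If the superseded row is set aside and all 10 early stoppers are assumed to have a value, the outer limits at 200 pg/mL are 6/108 = 5.6% to 12/108 = 11.1% on placebo and 15/107 = 14.0% to 19/107 = 17.8% on dexlansoprazole. The evidence in step 5 points to the low end.

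**The case against.** The strongest reply has four parts.

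**The samples are relabelled, not discarded.** SAP 5.13.2 plans baseline, post-baseline and change summaries, sets its hepatic and gastrin thresholds without tying them to Week 4, and lists all lab data. Markedly abnormal values in SAP 8.2.1 and 8.2.2 are described for the treatment period. This stands. A reader might infer that the windowing hides abnormal values in early stoppers, but during-treatment counts and listings need not be affected.

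**Table 8.c is transparent.** It prints its Week 4 denominators. This stands too. A reader might call the table a completers' table under a safety-set title. Equal counts do not prove that the same people are in both, and a by-visit row with its own N is ordinary practice.

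**The loss is smaller than it looks.** A reader might infer that all 10 early stoppers were dropped by the window, including the two per arm who stopped for treatment-emergent adverse events. The documents do not support that. Only about six omitted samples are evidenced, and the other four subjects may have had no sample for any window to recover. The stopping day, visit day and sample status of those who stopped for adverse events are not given.

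**A Days 2-35 window has a price.** It mixes shorter exposures, and samples taken a few days off drug, with true Week 4 values. Protocol 4.1 says gastrin rises over the first 3 months and returned to baseline within 7 days of the last dose in healthy volunteers, so the drug effect on gastrin could be diluted. This is a fair point about presentation. It is met by labelling the row Week 4/Final Visit and keeping the Days 22-35 figures beside it.

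None of this explains why labs have a window for a visit without labs. Unscheduled gastrin and repeat liver tests could give Day 2-21 values, but that does not justify moving a scheduled Final Visit sample out of the end-of-treatment summary.

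**Conclusion.** The inconsistency is real and minor. Table 5.a assigns labs and gastrin to a Week 2 visit that does not collect them, while ECG, on the same schedule, is handled correctly. Final Visit samples taken on or before Day 21 are absent from the Week 4 gastrin, shift and mean-change summaries, and no rule restores them.

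About 4 placebo and 2 dexlansoprazole subjects with a gastrin sample appear to be left out of Table 8.c. This assumes that the superseded row's denominators were subjects with any on-treatment gastrin value and that its percentages were rounded conventionally. The missing values could include unscheduled samples, which the text does not separate from Final Visit samples.

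The known effect on gastrin percentages is at most about 0.3 points. The effect on the shift and mean-change tables cannot be checked from the text. No safety conclusion is shown to change.

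**What to change.** In SAP Table 5.a, change two cells for safety labs and gastrin, matching ECG: Week 2 becomes NA, and the later window becomes Days 2-35, labelled Week 4/Final Visit. Keep the closest-to-scheduled-visit rule and the 7-day post-dose limit. For a subject whose samples all fall before Day 28, closest to Day 28 already means the latest sample, so no new selection rule is needed.

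Rerun the gastrin, shift and change-from-baseline tables with the number contributing per arm. Show the Days 22-35 gastrin figures alongside, so that dilution from short exposure or time off drug can be seen. Because results are already reported, record the change in SAP 5.15 as made after unblinding.

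The cost is two table cells, one row label and a rerun of the affected lab tables. No new data are needed. The downside is a more mixed Week 4/Final Visit row, which the parallel Days 22-35 figures address for gastrin.

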5.3 Analysis Sets

All efficacy analyses were performed on the full analysis set (FAS), which was defined as all randomized subjects who receive at least 1 dose of study drug and had post-baseline (post Day -1) data for the appropriate efficacy variable. The safety analysis set included all randomized subjects who received at least one dose of study drug.

5.4 Disposition of Subjects

A subject disposition summary was provided. Subjects' study completion data, including reasons for premature termination, were provided in listings and also summarized.

A summary of screening failures was also provided.

5.5 Significant Protocol Deviations

A summary of the number and percentage of subjects with a significant protocol deviation by type of deviation was provided using the safety analysis set. Individual subject listings of significant protocol deviations were provided.

5.6 Demographic and Other Baseline Characteristics

Demographic and baseline characteristics variables were summarized using the safety analysis set.

For continuous variables (age, weight, height, and body mass index [BMI]), summary statistics were generated.

For categorical variables, the number and percentage of subjects in each category was presented.

The following baseline characteristics were summarized.

- Number of days with daytime or nighttime heartburn between Study Days -8 and -2, inclusive.
- Number of days with nighttime heartburn between Study Days -8 and -2, inclusive.
- Number of days with daytime heartburn between Study Days -8 and -2, inclusive.
- Mean severity of daytime and nighttime heartburn between Study Days -8 and -2, inclusive.
- Mean severity of nighttime heartburn between Study Days -8 and -2, inclusive.
- Mean severity of daytime heartburn between Study Days -8 and -2, inclusive.
- Baseline severity of GERD symptoms as assessed by the investigator.
- Baseline number of days with daytime/nighttime rescue medication use.

5.7 Medical History and Concurrent Medical Conditions

Medical history and concurrent medical conditions were presented in a data listing and were summarized, count and percent, using the safety analysis set.

5.8 Medication History and Concomitant Medications

All medication history and concomitant medications were coded by therapeutic classification, sub classification, and medication using the World Health Organization Drug Dictionary (WHO Drug). A concomitant medication was defined as a medication that was ongoing as of Study Day 1, ends on or after Study Day 1, or starts on or after Study Day 1 and no more than 1 day after the last dose of study drug.

The number and percentage of subjects taking each concomitant medication was summarized for the safety analysis set. A subject with 1 or more concomitant medications within the same level of the WHODrug classification was counted only once in that level. WHODrug preferred term and therapeutic classification was used for summary:

- Medication history that the study subjects stopped taking within 90 days prior to the screening visit.
- Concomitant medications that started and stopped prior to baseline.
- Concomitant medications that started prior to and were ongoing at baseline.
- Concomitant medications that started after baseline.
- Concomitant medications that were ongoing at baseline and those that started after baseline.

5.9 Study Drug Exposure and Overdose

Overall study drug compliance (%) was determined as (total count of capsules taken / total number of days on study drug) \times 100%. The total number of days on study drug (exposure) was

calculated as date of last dose of study drug - date of first dose of study drug + 1, assuming no gaps in the dosing interval. Any gaps in dosing interval was ignored in the calculation of the total. If last dose date was missing, then 35 days were imputed as treatment period. Summary statistics for the total number of days on study drug and overall compliance were generated for the safety analysis set.

The number and percentage of subjects with overall study drug compliance of <80%, 80-<90%, and ≥90% was also summarized for the safety analysis set. Subjects with unreturned study drug were assumed to have taken 1 capsule of study drug for each day of exposure for the calculation of overall compliance. Subjects with overall compliance ≥100% were set to 100% in the analysis.

In addition, diary compliance was determined as the percentage of days during treatment with two diary entries:

$$\text{Diary Compliance} = \frac{\text{(Number of days with two diary entries collected during treatment period)}}{\text{(Number of days with two diary entries expected during treatment period)}} \times 100\%$$

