Additional endpoint: percentage of days without daytime heartburn during treatment		
N	108	107
Median	46.55	62.96

Source: [Table 15.2.1](#).

QD: once daily.

^a Percentage of days with neither daytime nor nighttime heartburn = (the days that are heartburn-free during treatment period) / (total number of days for which either a daytime or nighttime result is marked during treatment period) × 100%.

^b The 2-sided p-value was obtained using the Wilcoxon rank-sum test.

Table 7.b Subgroup Analyses of Percentage of Days With Neither Daytime Nor Nighttime Heartburn Over 4 Weeks (Full Analysis Set)

	Placebo QD N=108	Dexlansoprazole 30 mg QD N=107
Age (<45 years)		
N	46	50
Mean (SD)	39.40 (34.297)	53.09 (34.458)
P-value		0.068
Age (≥45 to 65 years)		
N	57	53
Mean (SD)	35.02 (29.633)	41.79 (36.018)
P-value		0.472
Age (≥65 years)		
N	5	4
Mean (SD)	37.17 (41.722)	45.37 (52.932)
P-value		0.898
Gender (Male)		
N	43	47
Mean (SD)	34.40 (33.307)	49.51 (37.033)
P-value		0.063
Gender (Female)		
N	65	60
Mean (SD)	38.70 (31.248)	45.40 (35.370)
P-value		0.381
BMI (<25 kg/m²)		
N	69	72
Mean (SD)	37.94 (31.249)	45.50 (36.638)
p-value		0.298
BMI (≥25 to 30 kg/m²)		
N	34	28
Mean (SD)	34.93 (33.229)	51.55 (36.338)
p-value		0.104
BMI (≥30 kg/m²)		
N	5	7
Mean (SD)	37.78 (40.352)	47.39 (30.665)
p-value		0.744

	Placebo QD N=108	Dexlansoprazole 30 mg QD N=107
H pylori status (positive)		
N	41	40
Mean (SD)	39.87 (30.941)	55.95 (35.893)
p-value		0.032
H pylori status (negative)		
N	67	67
Mean (SD)	35.22 (32.733)	41.99 (35.294)
p-value		0.403
Overall study drug compliance (<80%)		
N	0	1
Mean (SD)		0.00 (NA)
p-value		NA
Overall study drug compliance (80-<90%)		
N	1	3
Mean (SD)	83.33 (NA)	64.74 (37.701)
p-value		>0.999
Overall study drug compliance (≥90%)		
N	106	103
Mean (SD)	35.95 (31.370)	47.15 (35.884)
p-value		0.037

Source: Table 15.2.2.

Note 1: Percentage of days with neither daytime nor nighttime heartburn = (the days that are heartburn-free during Treatment Period)/(Total number of days for which either a daytime or nighttime result is marked during Treatment Period) * 100%.

Note 2: The p-value was obtained using the Wilcoxon rank-sum test.

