9.0 DISCUSSION AND OVERALL CONCLUSIONS

9.1 Discussion

Phase 3 studies performed in the United States have demonstrated positive results using dexlansoprazole capsules for heartburn relief in subjects with symptomatic nonerosive GERD. This study was the first to examine the efficacy and safety of dexlansoprazole capsules in Chinese subjects with symptomatic nonerosive GERD.

The main objective of this phase 3, double-blind, randomized study was to compare the efficacy of dexlansoprazole capsule (30 mg QD) and placebo in relief of daytime and nighttime heartburn over 4 weeks in Chinese subjects with symptomatic nonerosive GERD as assessed by daily electronic diary (eDiary).

No major differences in subject disposition were observed across treatment groups. Subject discontinuation rates in dexlansoprazole capsules groups (3.7%) were generally lower than placebo group (5.5%). Treatment compliance was high in all groups, with $\geq 97\%$ of the total 215 subjects maintaining greater than 90% compliance with the dosing schedule. Similarly, no major differences were observed across treatment groups in subject demographics. More females (58.1%) were enrolled in the study (consistent across treatment groups); however, this gender difference did not have an impact on the analysis of efficacy results. Approximately 51% of subjects were aged from 45 to 65 years. A small proportion of subjects were aged 65 years or older (4.2%); therefore, any interpretation of efficacy results in these subjects is limited.

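### Compliance in SAP 5.9 is measured only up to each subject's own last dose, so it does not support the Discussion's claims about keeping to the dosing schedule; at least 4 of 6 placebo discontinuers are in the ≥90% level

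*SAP*

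**What the plan says.** Section 5.9 of the SAP document (which also reports results) defines the measure: "Overall study drug compliance (%) was determined as (total count of capsules taken / total number of days on study drug", times 100%. The denominator is "calculated as date of last dose of study drug - date of first dose of study drug + 1, assuming no gaps in the dosing interval". Three further rules apply:

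- A missing last dose date: "If last dose date was missing, then 35 days were imputed as treatment period".
- Unreturned drug: "Subjects with unreturned study drug were assumed to have taken 1 capsule of study drug for each day of exposure".
- Values of 100% or more are set to 100%.

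Section 5.10.1 uses this variable, in levels <80%, 80-<90% and ≥90%, for a subgroup analysis of the primary endpoint.

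On disposition, section 6.1 reports: "A total of 10 subjects prematurely discontinued study drug, and 205 subjects completed all the study drug and planned study visits". Section 6.7 gives mean compliance above 99% in both arms and mean exposure of 26.8 days in each.

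The Discussion (9.1) describes at least 97% of the 215 treated subjects as "maintaining greater than 90% compliance with the dosing schedule". It then takes the ≥90% level (p=0.037, against p=0.057 for the primary analysis) as evidence of benefit when the medication is taken consistently.

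**The concern.** A dose omitted before the last dose lowers the ratio. A dose omitted after the subject stops enters neither numerator nor denominator. A subject who takes a capsule daily for a week and then stops is fully compliant by this formula, although treatment was planned for 4 weeks. That is a legitimate measure of intake while on drug, but it is not adherence to the planned schedule, which is how section 9.1 describes it.

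The label matters because the report relies on the variable. The ≥90% level is one of two subgroups with p<0.05 beside a non-significant primary result, and the Discussion gives it a causal reading. If the level includes subjects who stopped the drug, that reading does not describe the group analysed.

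**Working it through.** **Inputs.** Treated subjects by arm: section 6.3. Completers and discontinuers: Table 6.a. Compliance levels, means and SDs: Table 7.b.

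| | Placebo | Dexlansoprazole |
|---|---|---|
| Treated | 108 | 107 |
| Completed study drug | 102 | 103 |
| Discontinued study drug | 6 | 4 |
| ≥90% | 106 | 103 |
| 80-<90% | 1 | 3 |
| <80% | 0 | 1 |

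**Step 1: reproduce the report's figure.** (106 + 103)/215 = 209/215 = 97.2%, matching the stated 97% or more. Completers plus discontinuers equal the treated in each arm: 102 + 6 = 108 and 103 + 4 = 107. The placebo levels sum to 107, so one placebo subject has no level; this does not affect the bound below.

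**Step 2: discontinuers in the ≥90% level.** The minimum is max(0, number in level − completers). The maximum is the number of discontinuers.

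- Placebo: 106 − 102 = 4, so 4 to 6 of 6.
- Dexlansoprazole: 103 − 103 = 0, so 0 to 4 of 4.
- Both arms: 4 to 10 of 10.

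**Step 3: what the rule can hide.** Assume one capsule a day until stopping, and 28 planned doses purely for illustration.

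| Last dose on day | SAP 5.9 | Share of 28 doses |
|---|---|---|
| 7 | 100% | 25.0% |
| 14 | 100% | 50.0% |
| 21 | 100% | 75.0% |
| 25 | 100% | 89.3% |
| 26 | 100% | 92.9% |

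**Step 4: possible effect on the 97.2%.** If no completer changes level, the schedule-based share depends only on how many discontinuers leave:

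- none: 209/215 = 97.2%
- the 4 known from the counts: 205/215 = 95.3%
- all 10, if all are in the level: 199/215 = 92.6%

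**Step 5: possible effect on mean compliance.** If the 4 placebo subjects each score 100% now and all stopped at Day 14, the overall mean falls by 4 × 50/215 = 0.9 points.

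**Step 6: sensitivity of the ≥90% comparison.** The reported Wilcoxon p of 0.037 cannot be recomputed without subject data. A t-approximation from the summary statistics (placebo 106, mean 35.95, SD 31.370; dexlansoprazole 103, mean 47.15, SD 35.884) gives a difference of 47.15 − 35.95 = 11.2 points, p=0.017. The placebo sum is 106 × 35.95 = 3810.7. Removing 4 placebo subjects gives:

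- all four with 0% heartburn-free days: mean 3810.7/102 = 37.36, difference 9.8, p=0.038
- all four with 100%: mean (3810.7 − 400)/102 = 33.44, difference 13.7, p=0.003

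**The case against.** The strongest reply is that this is a disclosed convention. Discontinuations are in Table 6.a, exposure is in 6.7, and 9.1 gives the discontinuation rates (3.7% and 5.5%) in the sentence before the compliance claim. The ratio also fits the endpoint: for subjects who terminate early, section 5.10.1 ends the treatment period one day after the last dose, so diary outcome and compliance cover nearly the same days. This stands as a reason to keep the ratio under an accurate name. It does not make the ratio a measure of adherence to the schedule.

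A reader might infer that the tables prove misclassification, or scores of about 100%, for these subjects. They do not. They show only that at least four placebo discontinuers scored 90% or more. No stop day is given, and a stop at Day 26 or later would still reach 90% of 28 doses. The 35-day imputation for a missing last dose date can also lower a score: 14 capsules taken, with the rest returned, gives 14/35 = 40%.

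A third point also stands. Compliance arises after randomisation, although 5.10.1 lists it among baseline subpopulations. Moving discontinuers out of the ≥90% level would bring it closer to a completers-only comparison and increase selection. A schedule-based regrouping is therefore descriptive, not a better test of efficacy.

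**Conclusion.** The concern holds as a matter of labelling and interpretation. The 5.9 ratio ignores doses omitted after stopping, and at least 4 of the 6 placebo discontinuers are in the ≥90% level. That bound follows from the counts alone and needs no assumption about stop days. The claim about the dosing schedule and the reading of p=0.037 as the effect of consistent intake are not supported by this measure.

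How many subjects would leave the level is unknown. The 92.6% to 97.2% range rests on completers keeping their level.

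Two stronger conclusions are not available. The first is that the rule favoured dexlansoprazole: the bound is positive for placebo only, but dexlansoprazole could have up to 4 such subjects, and the diary values of the discontinuers in the level are not given. The second is that the subgroup result would be lost: in both extremes above the t-approximation stays below 0.05, and the Wilcoxon p cannot be recomputed. Neither the primary result (p=0.057) nor the secondary result (p=0.268) uses the compliance formula.

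**What to change.** 1. In 5.9, name the present ratio compliance while on study drug, and use that name wherever it is reported.
2. In 9.1, replace the reference to the dosing schedule accordingly, state by arm how many discontinuers are in the ≥90% level, and withdraw or qualify the statement about consistent intake.
3. Add a supplementary schedule-based compliance line with one planned-dose denominator rule for completers and early stoppers alike. Mixed rules would classify equal intake differently: 25 doses would score 25/25 = 100% for a completer seen early in the ±3-day window and 25/28 = 89.3% for an early stopper.
4. Before fixing that denominator, reconcile the protocol on the last dosing day. Section 8.1.3 puts the last dose on the day before the Final Visit, but also has a dose taken on the day of the fasting laboratory visit, and footnote (d) of Appendix A has the dose taken on the morning of the visit.
5. Rerun Table 15.1.14 and the compliance rows of Table 7.b as a supplement labelled post hoc, since unblinded results are already known.

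The cost is some rewording, a small rerun on data already collected, and a compliance figure that may be slightly less favourable.
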